The primary efficacy objective for this study is to evaluate the treatment effect of ocrelizumab compared with placebo on delaying the time to development of new radiologic or clinical evidence of MS.

Primary Efficacy Endpoint:

Time to development of first new radiologic (e.g., new or enlarging T2 lesions, T1 gadolinium-enhancing lesions consistent with MS) or clinical evidence of MS (i.e., neurological event resulting from CNS demyelination, as evidenced by acute or progressive clinical syndrome consistent with MS).

A detailed description of the primary endpoints and estimands are provided in Section 6.4.1.

SECONDARY OBJECTIVE(S)

Secondary Efficacy Objective

The secondary objectives for this study are to understand the treatment effect of ocrelizumab compared with placebo on clinical, neuroimaging and serum neurofilament light (NfL) biomarkers that are associated with disease activity, and with the clinical response to ocrelizumab.

Secondary Efficacy Endpoints:

Cumulative number of new or enlarging T2 lesions identified at Weeks 48, 104 and 208

Change in T2-lesion volume from Baseline to Weeks 48, 104 and 208

Cumulative number of new T1 gadolinium-enhancing lesions identified at Weeks 48, 104 and 208

Change from Baseline to Weeks 48, 104 and 208 in total brain volume

Change from Baseline to Weeks 48, 104 and 208 in total spinal cord volume

Change from Baseline to Weeks 48, 104 and 208 in serum NfL (sNfL)

Exploratory Efficacy Objectives

The exploratory objectives for this study are to evaluate inflammatory, neurodegenerative, and exploratory biomarkers of disease activity in the blood and cerebrospinal fluid (CSF) and their correlations with radiologic, clinical and patient reported outcomes.

Exploratory Efficacy Endpoints:

Change from Baseline to Weeks 48, 104 and 208 in white matter volume, gray matter volume, and thalamic volume

Change from Baseline to Weeks 48, 104 and 208 in spinal cord white and gray matter volume

Change from Baseline to Week 104 and 208 in CSF immune cell populations frequency and phenotype

Change from Baseline to Week 104 and 208 in CSF NfL levels

Percent change in the presence of CSF oligoclonal bands (OCB) from Baseline to Weeks 104 and 208

Percent change in normalization of CSF IgG index from Baseline to Weeks 104 and 208

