Change from Baseline to Weeks 104 and 208 in CSF biomarkers (i.e., CSF Weeks 104 and 208 only), including CXCL13, BAFF (B cell activating factor), TNF, IL-6, IL-10, IL-17, interferon-gamma, IL-4, IL-23, IL-8, soluble CD27 (sCD27), genetic risk factors (HLA-DRB1*15:01) or other emerging exploratory markers of disease biology as appropriate

Change from Baseline to Weeks 48, 104, and 208 in slowly evolving lesions (SEL)

Change from Baseline to Weeks 24, 48, 72, 104, 130, 156, 182 and 208 in peripheral blood immune cell population frequency and phenotype, including B cells, T cells and innate immune cells (monocyte, macrophage, neutrophils, natural killer cells, etc.)

Change from Baseline to Weeks 24, 48, 72, 104, 130, 156, 182 and 208 in peripheral blood biomarkers, including CXCL13, BAFF (B cell activating factor), TNF, IL-6, IL-10, IL-17, interferon-gamma, IL-4, IL-23, IL-8, soluble CD27 (sCD27), genetic risk factors (e.g., HLA-DRB1*15:01) or other emerging exploratory markers of disease biology as appropriate

Change from Baseline to Weeks 24, 48, 72, 104, 130, 156, 182 and 208 in patient reported outcomes, including quality of life, fatigue, depression, and disability, as measured by Neuro-QoL™

Change from Baseline to Weeks 24, 48, 72, 104, 130, 156, 182 and 208 in cognitive function and information processing speed as measured by symbol digit modality test (SDMT)

Correlation between changes in compartment-specific biomarkers of disease biology with radiologic and/or clinical disease outcomes

Correlation between changes in patient reported outcomes, including SDMT, and radiologic and/or clinical disease outcomes

Correlation between changes in compartment-specific immune cell subsets with radiologic and/or clinical disease outcomes.

Correlation between changes in NfL levels and radiologic and/or clinical disease outcomes

Correlation between changes in CSF abnormalities (OCB and IgG index) and radiologic and/or clinical disease outcomes

SAFETY OBJECTIVES

The safety objectives for this study are to evaluate the safety of ocrelizumab compared with placebo on the basis of the following endpoints:

Nature, frequency, severity, and timing of adverse events

Vital signs, physical findings, and clinical laboratory results during and following study drug administration

Adverse events related to biomarker sample collection

STUDY DESIGN

DESCRIPTION OF THE STUDY

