Results of a lumbar puncture/CSF oligoclonal banding analysis performed at baseline are required prior to randomization. A subset of study participants may have had lumbar puncture/CSF analysis performed previously. Such historic oligoclonal banding results may be used for the purpose of stratifying randomization with appropriate source documentation. For study participants who have previously had lumbar puncture/CSF analysis, all study lumbar punctures are optional.

For study participants who have never had a lumbar puncture/CSF analysis, this procedure is required prior to randomization. Additional lumbar punctures at weeks 104 and 208 are optional.

Blinding

This is an assessor blinded study. During the double-blind period, each site will have: a principal or Treating Investigator and an Examining Investigator or rater. Both the Treating and Examining Investigators will be blinded to treatment assignment.

The Treating Investigator is the physician responsible for the patient care and should be a neurologist experienced in the care of MS patients. The Treating Investigator will make treatment decisions based on the patient's clinical response and laboratory findings.

The Examining Investigator should be a neurologist or other health care practitioner and must be trained in administering the Neurostatus Functional System Scores (FSS) and Expanded Disability Status Scale (EDSS) examination prior to study start (Appendix 5).

The Examining Investigator will perform the neurological examination, document the FSS scores, and assess EDSS scores. The Examining Investigator or a qualified designee will also be responsible for performing and documenting results from the Symbol Digit Modalities Test. They will only have access to data from the assessments listed above. Every effort will be made to ensure that there is no change in the EDSS rater throughout the course of the study for any individual patient. Whenever possible, the same person should perform the examination for the full study duration.

All efforts should be made to keep the Examining Investigator blinded to the treatment assignment during the double-blind period. Patients will be instructed not to discuss any symptoms related to the study treatment with the Examining Investigator; the Examining Investigator should remind the patient at the start of the examination.

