CSF: A CSF specimen will be collected at baseline for all participants who have not previously undergone this testing. CSF will be tested for cell count, protein, elevated IgG index and one or more IgG oligoclonal bands using the local lab. The remainder of this CSF sample will be retained as a biomarker sample, and analysis may include, but will not be limited to NfL and adaptive and innate immune cell subsets. Levels of soluble neurodegeneration markers, and/or inflammatory markers; and the relationship between ocrelizumab exposure and selected pharmacodynamics. Fluoroscopy can be used, if required, for the LP to draw the CSF.

Certain analyses may be conducted at study sites as directed by the Sponsor, or the sample may be shipped to the central laboratory and/or to the Sponsor or designated processing site, and may be processed by the Sponsor's laboratory or the Sponsor's qualified designated laboratory (CRO and/or academic research laboratories affiliated with the study).

For sampling procedures, storage conditions, and shipment instructions, see the laboratory manual.

Biological samples will be destroyed when the final Clinical Study Report has been completed, with the following exceptions:

Plasma and/or serum and/or whole blood samples or their derivatives (e.g. peripheral blood mononuclear cells, PBMC) collected for biomarker research will be destroyed no later than 5 years after the final Clinical Study Report has been completed unless the patient has consented for their transfer to the Research Biosample Repository (RBR, described in Section 4.5.19 below).

Any leftover CSF samples that were collected for IgG index/OCB analysis to determine eligibility for patients who did not have historical data and the Week 48 CSF sample will be destroyed no later than 5 years after the final Clinical Study Report has been completed or until exhausted, or earlier depending on local regulations unless the patient has consented for their transfer to the RBR.

Oral samples (gingival swabs) will be destroyed no later than 5 years after the final Clinical Study Report has been completed or until exhausted, or earlier depending on local regulations unless the patient has consented for their transfer to the RBR.

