Population-level-summary estimator: The hazard ratio from a stratified Cox-proportional hazards model will be used. The stratified log-rank p-value will be used to test for statistical significance. Both will be stratified by the factors specified (see Section 4.2.1) for randomization.

Handling of missing data:

Withdrawal from study: a patient will be censored at the time of withdrawal from study.

Missing assessments at scheduled visits prior to last assessment: Missing data at scheduled visits prior to last assessment will not be imputed.

Secondary Efficacy Endpoints

The secondary endpoints for this study are to evaluate the efficacy and impact of ocrelizumab compared with placebo on the basis of the endpoints as described in Section 2.2.1 and biomarkers of disease activity and neuroaxonal damage in peripheral blood.

Each change from baseline for continuous secondary endpoints will be tested and analyzed using a stratified mixed-effects model for repeated measures (MMRM)

assuming missing at random (MAR). Sensitivity analyses will be conducted to assess the validity of this assumption,

For MRI related count endpoints (cumulative number of T2 lesions and T1 gadolinium-enhancing lesions), generalized linear methods appropriate for count data will be used depending on the distribution of the counts, e.g., a stratified negative binomial regression model.

Estimands for the Secondary Analyses

The estimands for the remaining secondary endpoints will have the same population and handling of missing data attributes as for the primary analysis.

Exploratory Efficacy Endpoints

Analyses on exploratory efficacy endpoints will be performed as data allows.

Exploratory efficacy endpoints are listed in Section 2.2.2. Further details will be described in the SAP.

SAFETY ANALYSES

The safety analysis population will consist of all randomized patients who received at least one dose of study drug, with patients grouped according to treatment received.

Safety will be assessed through summaries of exposure to study treatment, adverse events, changes in laboratory test results, and changes in vital signs and ECGs. Study treatment exposure (such as treatment duration, total dose received, and number of cycles and dose modifications) will be summarized with descriptive statistics.

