All verbatim adverse event terms will be mapped to MedDRA thesaurus terms, and adverse event severity will be graded according to CTCAE v5.0 grade. All adverse events, serious adverse events, adverse events leading to death, adverse events of special interest, and adverse events leading to study treatment discontinuation that occur on or after the first dose of study treatment (i.e., treatment-emergent adverse events) will be summarized by mapped term, appropriate thesaurus level, and severity grade. For events of varying severity, the highest grade will be used in the summaries. Deaths and cause of death will be summarized.

Associated laboratory parameters, such as hepatic function, renal function, and hematology values, will be grouped and presented together. Marked abnormalities will also be flagged.

BIOMARKER ANALYSES

Biomarkers will be assessed at baseline (screening) and subsequent time points following administration of ocrelizumab or placebo. Biomarkers levels at baseline or over time may be compared with efficacy or safety measurements to assess prognostic or

predictive properties. Biomarkers may also be analyzed over time as absolute values and/or percent change relative to baseline over time, and may be compared with efficacy, other biomarkers, or safety measurements.

INTERIM ANALYSES

The iDMC will review interim analyses as specified in the iDMC Charter. Interim analyses will be conducted by the unblinded statistician(s) and will focus on recruitment/enrollment, study conduct and safety.

No formal interim analyses for futility or efficacy are planned. However, the aggregate rate of the primary outcome will be monitored throughout the study to assure a sufficient number of events. The following scenario may trigger an interim look for futility.

If we are not on target to reach the hypothesized number of events (in the blinded dataset) by the end of the follow-up period, we will assess whether an extension to follow-up is fiscally feasible. If follow-up is feasible, a non-binding futility analysis using an alpha-spending function will be conducted to determine whether it is worth extending follow-up.

Similarly, we will monitor the current trend of treatment in this patient population. The following scenario may trigger an interim look for efficacy if applicable.

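### The only listed between-arm endpoint for the CSF IgG index is a normal/abnormal classification of a continuous ratio, with no cut-off or denominator; baseline-adjusted change would usually use scarce samples better

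*Combined protocol and SAP*

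**What the plan says.** Section 2.2.2 of the protocol lists, among the exploratory efficacy endpoints, "Percent change in normalization of CSF IgG index from Baseline to Weeks 104 and 208". It sets no upper limit of normal and does not say whether the percentage is taken over all sampled patients or only over those abnormal at baseline. The section on laboratory, biomarker and other biological samples has CSF tested for "elevated IgG index and one or more IgG oligoclonal bands using the local lab".

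The index appears in one other listed endpoint: "Correlation between changes in CSF abnormalities (OCB and IgG index) and radiologic and/or clinical disease outcomes". That relates the index to outcomes and does not compare the arms.

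Two general statements apply. Under Biomarker Analyses: "Biomarkers may also be analyzed over time as absolute values and/or percent change relative to baseline over time". Under Exploratory Efficacy Endpoints in the statistical section: "Analyses on exploratory efficacy endpoints will be performed as data allows", followed by "Exploratory efficacy endpoints are listed in Section 2.2.2. Further details will be described in the SAP".

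On sample numbers, the Treatment Assignment section says of patients with no previous CSF analysis: "Additional lumbar punctures at weeks 104 and 208 are optional". For patients with a previous analysis, every study lumbar puncture is optional. The expected number of follow-up punctures is not stated.

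**The concern.** In the same list, CSF NfL, CXCL13, BAFF and the cytokines are all defined as change from baseline. Oligoclonal bands are handled as present or absent, which is natural for them. The IgG index is the one quantitative CSF marker in the list that is reduced to a classification, and no reason is given.

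A cut on a continuous ratio counts a large fall that stays above the limit as no change, and a trivial fall across the limit as a success. With testing at local laboratories and no common limit, the cut may also differ between sites.

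The background sections name an elevated index as a possible risk factor for conversion, and intrathecal antibody production is part of the rationale for ocrelizumab. Each paired value costs a patient an optional lumbar puncture. What is at stake is how much can be learned from a small set of invasive samples. No decision of the trial depends on this endpoint.

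**Working it through.** **1. Is a continuous between-arm comparison prespecified anywhere?**
- Section 2.2.2, endpoint line: between-arm, classified.
- Section 2.2.2, correlation line: changes in the index, but against outcomes.
- Biomarker Analyses: absolute values or percent change are allowed, worded as an option.
- Exploratory Efficacy Endpoints: detail deferred to the SAP.

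So a continuous analysis is permitted, but none is committed to.

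**2. A figure to reproduce.** There is none. The documents give no SD, effect, abnormal fraction, cut-off or number of follow-up punctures for this endpoint.

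**3. Assumed inputs (none from the documents except N, the allocation ratio and dropout).** Log index normal with SD 1 and cut at 0; baseline mean Φ⁻¹(f), with f the fraction abnormal at baseline; follow-up = mean + ρ(baseline − mean) + √(1 − ρ²)·error − δ in the treated arm; two-sided 5%; 1,500 simulated trials per cell, so the simulation error is at most √(0.25/1500) = 1.3 percentage points. The largest sample, 33 per arm, is 50 × 0.9⁴ = 32.8: half of about 100 patients, 10% annual dropout over four years, and every retained patient accepting the optional puncture.

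**4. Results at 20 pairs per arm, δ = 0.5 SD in every treated patient, ρ = 0.6-0.8, f = 0.5-0.7.**

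| Analysis | Power |
|---|---|
| Continuous, adjusted for baseline | 48-74% |
| Normalized, baseline-abnormal only: Fisher / chi-square | 11-14% / 19-22% |
| Normal at follow-up, all patients: Fisher / chi-square | 14-16% / 22-25% |

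**5. Wider grid, ρ = 0.7, f = 0.4-0.8, chi-square for the binary versions.**

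| Pairs per arm, δ | Continuous | Baseline-abnormal only | All patients |
|---|---|---|---|
| 10, 0.5 | 0.30-0.33 | 0.09-0.12 | 0.09-0.14 |
| 10, 0.8 | 0.62-0.65 | 0.18-0.24 | 0.19-0.25 |
| 20, 0.5 | 0.55-0.60 | 0.17-0.22 | 0.20-0.25 |
| 20, 0.8 | 0.93 | 0.35-0.47 | 0.46-0.50 |
| 33, 0.5 | 0.79-0.81 | 0.25-0.30 | 0.33-0.42 |
| 33, 0.8 | 0.99 | 0.53-0.69 | 0.68-0.74 |

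Relative loss, baseline-abnormal only: from 1 − 0.687/0.994 = 31% to 1 − 0.087/0.303 = 71%. All patients: from 1 − 0.741/0.995 = 26% to 1 − 0.185/0.626 = 70%.

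**6. Hand check at 20 per arm, δ = 0.5, ρ = 0.7, f = 0.6.**
- Continuous: residual SD √(1 − 0.49) = 0.714. Then 0.5/0.714 × √(20/2) = 2.21, and Φ(2.21 − 1.96) = 0.60 (simulated 0.604).
- Binary, 0.6 × 20 = 12 baseline-abnormal patients per arm, simulated normalization rates 0.20 and 0.42: SE = √(0.31 × 0.69 × 2/12) = 0.189. Then 0.22/0.189 = 1.17, and Φ(1.17 − 1.96) = 0.21 (simulated 0.223).

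**7. Shift only in patients abnormal at baseline, binary test confined to them.**
- 20 per arm, 0.5 SD: continuous 17-41%, chi-square 16-21%, Fisher 11-13%. At f = 0.5, continuous 17-21% against chi-square 19-20%: no gain.
- 33 per arm, 0.8 SD, f = 0.5, ρ = 0.6: continuous 49%, Fisher 48%, chi-square 56%.

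With all sampled patients in the denominator, the continuous analysis was higher in every cell under either pattern of shift.

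**The case against.** Three stronger readings are tempting, and the documents support none of them.

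*That the index is analysed only as normalization.* The Biomarker Analyses section allows absolute values, the correlation endpoint uses changes in the index, and detail is left to the SAP. That rules out the word only. It remains true that no continuous between-arm comparison is prespecified.

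*That patients with a normal baseline drop out.* A reader might infer this, because only an abnormal value can normalize. But no denominator is stated, and the wording leans the other way: among baseline-abnormal patients the proportion normal at baseline is zero, so a percent change from baseline would be undefined. The parallel line for oligoclonal bands also reads most naturally as a proportion of everyone sampled.

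*That most of the power is lost.* This rests on inputs the documents do not give. Even with a uniform shift, the loss at 33 per arm and 0.8 SD is 31-47% against the baseline-abnormal test. A uniform shift also favours the continuous analysis, since it lets already-normal values fall as much as abnormal ones. Step 7 shows the gain disappearing under a different, equally plausible assumption.

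Two further points stand. At 10 pairs per arm and 0.5 SD, the continuous analysis has only 24-43% power across ρ = 0.6-0.8, so it too would usually show no difference. And a numeric index may not exist for every patient. The laboratory section lists it, but the lumbar-puncture footnote to the Schedule of Activities (Appendix 1) omits it from local CSF testing, and the Description of the Study accepts historical CSF results for oligoclonal banding.

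**Conclusion.** The point holds as a low-cost improvement to one exploratory endpoint. The only listed between-arm measure of the IgG index is a classification without a cut-off or denominator, while the comparable quantitative CSF markers are measured as change from baseline. Under a uniform shift the continuous analysis was more powerful in every cell run, whichever denominator and test were used. At 20 pairs per arm and 0.5 SD the difference is about 48-74% against 11-25%.

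Those figures are illustrative. They depend on the assumed effect, correlation, abnormal fraction and number of pairs, and on treatment shifting all patients alike. If only baseline-abnormal patients respond and the binary test is confined to them, the advantage can disappear. The plan claims no power for this endpoint, so nothing it states is contradicted.

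**What to change.** In Section 2.2.2, define the endpoint as change in CSF IgG index from baseline to Weeks 104 and 208. In the SAP, analyse the log index at follow-up with the patient's own baseline log index and the randomization strata (spinal cord lesions, oligoclonal bands) as covariates, in all patients with paired numeric values. Keep the proportion with a normal index as a descriptive summary, with its cut-off and denominator stated.

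Reconcile the Description of the Study, the laboratory section and the Appendix 1 footnote on whether the index is measured and recorded as a number at baseline and follow-up, including for patients who enter on historical CSF results.

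The cost is one line of endpoint wording and one SAP model. Where the index is measured, no extra sample or procedure is needed. The headline becomes a ratio of geometric means, which is less familiar than a percentage, and the analysis covers only patients who have a numeric baseline index.

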Appendix 2. For the sub-study schema, please refer to **Appendix 3**

This is a multicenter, randomized, double-blind, placebo-controlled, Phase 4 study in which eligible patients with RIS (as defined by meeting 2017 McDonald criteria for DIS) will be randomized 1:1 to receive ocrelizumab treatment or placebo (standard of care). Three courses of ocrelizumab or placebo will be administered over the course of the study. The first course of ocrelizumab will be administered as two 300 mg infusions at Week 0 (Day 1) and Week 2 (Day 15), with the subsequent second- and third-courses given as a single 600 mg infusion at Weeks 24 and 48. Placebo will be administered at the same timepoints. Screening will occur over a 45-day period.

All participants must have had CSF analysis at baseline. For those who have had lumbar puncture and CSF analysis prior to screening for this study, historical results (for oligoclonal banding) will be accepted as long as original source documentation can be provided. Optional CSF (baseline, weeks 104 and 208, with paired blood) can still be contributed to the study. For those who have not had prior CSF analysis, lumbar puncture and CSF analysis will be required at baseline with two optional follow-up lumbar punctures post-baseline (Weeks 104 and 208). Refer to Figure 1 Study Schema.

The double-blind phase will be considered complete when the results of the primary analysis are disclosed and the study becomes unblinded to sites. If the projected number of radiological or clinical events (21) has not been reached when the last patient completes 4 years in the double-blind phase because of slower than anticipated event rates, the double-blind phase may be extended until the required number of events have occurred. After the primary analysis is complete, patients will remain in the study and be followed for a minimum total of 3 years after treatment.

As the primary analysis is event driven, the study duration in the double-blind phase will vary for each patient.

The study population will consist of patients with RIS, defined as individuals with magnetic resonance imaging (MRI) anomalies within the CNS that are typical of CNS inflammatory demyelinating disease, yet lacking symptomatic clinical features suggestive of MS. To more closely approximate real-world practice and facilitate early diagnosis, MRI anomalies will be required to meet dissemination in space criteria as defined by the 2017 McDonald diagnostic criteria for MS. Male and female patients aged 18–55 with a diagnosis of RIS in accordance with the McDonald 2017 criteria for DIS at screening will be eligible for this study.

As RIS is typically identified incidentally, first-degree family members of individuals with MS will be pre-screened for possible recruitment into this study. These relatives are at increased risk for RIS, with an estimated 3%–10% of clinically unaffected siblings having lesions highly suggestive of demyelination. After obtaining written consent, pre-

screening MRIs will be offered to such high-risk individuals and those who meet radiologic criteria will be eligible for the full study. Patients already diagnosed with RIS are also eligible for this study. Any known RIS patients whose MRIs have remained stable for 5 years or more will be excluded.

While younger age (<37) represents a significant predictor for the development of a first clinical event in RIS patients, RIS is often not diagnosed until later; indeed, in the recent ARISE clinical trial of RIS, the average age at diagnosis was around 44 years old (Okuda et al, 2022). Moreover, the ARISE trial found recruitment to be difficult and ultimately needed to end the study early for this reason. In order to effectively recruit for the CELLO trial, we will use the age range of 18-55, aligning with the phase 3 ocrelizumab trials in multiple sclerosis as well as the recent published study of RIS.

Pre-screened first degree family members who do not meet the McDonald 2017 criteria for DIS will be eligible to participate in a registry (Appendix 4). These individuals will have annual phone check-ins over the course of the total study duration to assess patient reported outcomes (Neuro-QoL; see Appendix 10) and healthcare utilization including neurologic or other autoimmune diagnoses, symptoms, medications (i.e., prescriptions, over-the-counter, supplements, etc.), number of emergency department visits, hospitalizations, office visits/physician encounters (i.e., specialists), etc.

Re-screening in general is not allowed, however patients enrolled in the registry may qualify for a re-screening opportunity at the discretion of the investigator. For more details on the registry of first-degree family members of patients with MS, see Appendix 4.

In the case of a clinical neurologic event consistent with CNS demyelination, the patient should have an unscheduled visit and a full assessment, as detailed in the SOA. Upon confirmation of a clinical relapse, the patient will be discontinued from the study and should start commercially available DMT, including ocrelizumab, at the discretion of the treating physician. In the event of radiologic progression, in which a new lesion suggestive of MS develops, the choice to continue or discontinue from the study in order to initiate treatment is at the discretion of the treating physician.

Treatment may be stopped at any time due to lack of clinical benefit, unacceptable toxicity, withdrawal of consent, patient or physician decision to discontinue treatment, death, or if the sponsor decides to close the trial, whichever occurs first.

[figure not shown]
An external, independent DMC (iDMC) will periodically review safety data throughout the study until the primary analysis is performed. Following unblinding, iDMC involvement in safety monitoring is no longer needed. Analyses required for the iDMC data review will be performed as described in the iDMC Charter.

All patients enrolled into the main study will be evaluated for safety throughout the study. In the case of early termination, the patient will be asked to return for an early termination visit.

Patients who do not meet the criteria for participation in this study (screen failure) may qualify for one re-screening opportunity (for a total of two screenings per participant) at the investigator's discretion. The investigator will record reasons for screen failure in the screening log. Family members who undergo radiologic pre-screening and do not have lesions meeting DIS criteria are not considered screen failures and will be enrolled in the family registry.

[Figure 1](#) presents an overview of the study design. A schedule of activities is provided in [Appendix 1](#).

Figure 1 Study Schema

Tx=treatment; * = primary endpoint is event driven therefore patients may be unblinded after reaching primary endpoint

Confidential — For internal use only. Do not copy, distribute or use without prior written consent.

1

END OF STUDY AND LENGTH OF STUDY

The end of this study is defined as the date when the last patient, last visit (LPLV), occurs or the date at which the last data point required for statistical analysis or safety follow-up is received from the last patient, whichever occurs later. The end of the study is expected to occur 48 months/4 years after the last patient is enrolled.

In addition, the Sponsor and/or Collaborator (Genentech) may decide to terminate the study at any time.

The total length of the study, from screening of the first patient to the end of the study, is expected to be approximately 6–7 years.

RATIONALE FOR STUDY DESIGN

Rationale for Ocrelizumab Dose and Schedule

Consistent with the USPI, the ocrelizumab dose administered in this study is 600 mg every 24 weeks. Three-courses of ocrelizumab or placebo will be administered over the course of the study. The first dose of ocrelizumab will be administered as two 300 mg IV infusions on Week 0 (Day 1) and Week 2 (Day 15), with the subsequent second- and third-courses given as a single 600 mg infusion at Weeks 24 and 48. Study drug for patients randomized to the placebo group will be administered analogously to those receiving ocrelizumab. Patients will then be followed in the clinical trial for 3 years.

Administering three-courses of ocrelizumab permits the interrogation of the immunodynamics surrounding the emergence of CNS autoimmunity and the reconstitution of the immune system following anti-CD20 B cell depletion with ocrelizumab. Understanding the effect of B cell depletion in RIS using this treatment paradigm will provide invaluable insight into the onset of MS, as well as the mechanism of action of ocrelizumab, both of which remain poorly understood.

Rationale for Patient Population and Use of 2017 McDonald Criteria

When considering the pathophysiology of MS, and the increased emphasis placed on earlier identification of MS in order to initiate appropriate treatment early, it has been recommended that identical MRI criteria for DIS should be applied for the diagnosis of RIS and MS (De Stefano et al 2018; Flippi et al 2016). The original criteria for RIS required a fairly heavy lesion burden, whereas it has been suggested that RIS diagnostic criteria should instead reflect the 2017 McDonald criteria for DIS, which are routinely used for the clinical diagnosis of MS (Table 1). The McDonald criteria were revised in 2017 to increase sensitivity while promoting more rapid diagnosis of MS. In contrast to Okuda criteria, the McDonald criteria require fewer lesions and instead focus on lesion location rather than lesion count for the assessment of DIS, which facilitates interpretation and use in scenarios suggestive of MS. Therefore, the McDonald 2017 criteria for DIS represent the “real-world” criteria used routinely in everyday practice to establish MS diagnosis and share comparable sensitivity in detecting RIS, perhaps at even earlier stages of pathology. Patients meeting McDonald 2017 criteria for DIS can be confirmed to have MS at the time of their first clinical symptoms of disease. Early recognition of the disease provides the best window for treatment intervention. Thus, utilizing the 2017 McDonald criteria for DIS to establish RIS in this study may have clinical and research implications, not only in establishing an earlier window of opportunity to identify, diagnose and treat, but also in advancing the understanding of the onset and pathogenesis of disease.

Rationale for Control Group

To date, there are no expert guidelines on the management of RIS. The standard of care for RIS patients is active monitoring with periodical clinical and radiological follow-up every 6–12 months. This is in accordance with the MAGNIMS consensus recommendation published in 2018. Given that no standard of care therapy exists for the treatment of RIS, a placebo-control is considered to be appropriate for this trial.

Rationale for Biomarker Assessments

There is a paucity of evidence-based guidelines on the management of RIS and of factors that stratify risk for clinical MS in this population. Therefore, the discovery of biomarkers predictive of clinical conversion can guide clinical treatment decision-making, ultimately leading to risk-stratification for therapeutic interventions that maximize clinical benefit while minimizing patient harm. The identification of biomarkers reflecting MS disease biology in RIS not only represents a critical opportunity to better understand disease onset and progression, it also permits interrogation of the mechanism of action of ocrelizumab in this population.

Several studies have investigated biomarkers and risk factors associated with the development of a first clinical event in RIS patients. The presence of spinal cord lesions portends the greatest risk of conversion to clinical MS to date. Age (<40), sex (male) and the presence of infratentorial brain lesions have also been identified as putative risk factors to predict conversion to MS in RIS patients (Okuda et al. 2011, 2014; Etemadifar et al. 2014; Makhani et al 2019; Thouvenot et al. 2019). Abnormal CSF findings, including the presence of OCBs and/or elevated IgG index, have also been suggested as additional risk factors (Gastaldi 2017; Nakamura et al. 2014; Matute-Blanch et al. 2018; Makhani et al. 2019).

In the context of MS, biomarkers from the CSF are utilized as a surrogate for the CNS tissue (Comabella and Montalban 2014) and MRI of the brain and spinal cord is used as a non-invasive surrogate marker of disease activity (e.g., contrast-enhancing lesions; new and enlarging T2-weighted lesions). In particular, spinal cord MRI provides important additional information to brain MRI in understanding MS pathophysiology, allowing more accurate and earlier diagnosis of MS, and in identifying MS patients at higher risk of developing more severe disability. Advances in MRI techniques have enabled assessment of brain and spinal cord area and volumes. Changes in global and regional brain and spinal cord area (i.e., white and gray matter, thalamus) can be detected early in the disease course and are highly associated with disability progression and severity in MS as well as quality of life measures, including cognition and fatigue.

Studies have also focused on the evaluation of fluid biomarkers in RIS reflecting MS disease biology and suggest that these may also provide predictive value. In clinically definite MS, NfL has emerged as a leading candidate biomarker in blood and CSF. NfL correlates with disease activity, including Gd-enhancing MRI lesions and clinical relapses (Burman et al. 2014), as well as treatment response in RMS and PPMS (Gunnarsson et al. 2011; Axelsson et al. 2014). High levels of NfL in the CSF (Matute-Blanch et al 2018) and serum (Bjornevik et al 2019), have been identified in individuals with RIS and are associated with increased risk for the development of a first clinical neurologic event. Other key biomarkers of disease biology in MS that may be relevant to RIS include the presence of OCBs, or antibodies produced in the CSF (Link and Huang 2006), as well as the presence of intrathecal memory B cells, plasmablasts (Cepok et al. 2005), and the potent B cell chemoattractant CXCL13 (Piccio et al. 2010; Bankoti et al. 2014; Palanichamy et al. 2014; Stern et al. 2014). The presence of OCBs has been associated with a worse prognosis (Joseph et al. 2009; Winger and Zamil 2016) and has been shown to have high predictive value for conversion from CIS to clinically definite MS (Tintore et al 2008; Dobson et al 2013), which may also be relevant to those with RIS (Matute-Blanch et al. 2018). Furthermore, it has been observed that the peripheral B cells of RIS patients are skewed toward a proinflammatory phenotype and are associated with worse prognosis. However, these biomarkers require further investigation in RIS as prior studies had relatively small sample size and short follow-up periods.

